4.5 Reference Therapy (Usual Care) and Intervention Treatment

4.5.1 Usual Care: Haemodialysis Renal Replacement Therapy

Haemodialysis is the most common dialysis (renal replacement) treatment for kidney failure, usually involving three dialysis sessions a week, and each lasting around 4 hours. In addition to the dialysis procedure itself, patients receive a number of management interventions, including blood pressure control, treatment of anaemia, phosphate control, and cardiovascular risk mitigation strategies. They may also receive dietary advice, counselling, input from social workers, and other forms of educational support. Many of the patients take renin-angiotensin blockers which are believed to afford cardiovascular protection. Aspirin and/or cholesterol-lowering therapies may be prescribed in an attempt to further reduce cardiovascular risk. Anaemia is treated by the use of erythropoietin replacement therapy and intravenous iron supplementation. Phosphate control is achieved by both dietary advice and the use of phosphate binders. For the purposes of this trial, we suggest that usual care, in both arms of the trial, should allow all of these other treatments so that we are

investigating any additional benefit of the intra-dialytic exercise training intervention to usual care.

4.5.2 Planned Intervention: Intra-dialytic Exercise Training

The intra-dialytic exercise prescription will be based on current Physical Activity (PA) guidelines for the elderly (28) and for people with diabetes (29) and cardiovascular disease (30). These recommend a minimum target amount of 1000 kcal per week be expended in PA for health benefits with optimal benefits associated with weekly target PA accumulation of 1500 to 2000 kcal. As opportunity for structured prescribed exercise is largely restricted to patients' three haemodialysis days the eventual aim is for the patients to accumulate as great a proportion of this minimum threshold level of 1000 kcal per week via intra-dialytic exercise. Peak aerobic capacity assessment will be conducted to derive and individualise the exercise prescription. Using a modified cycle ergometer, aerobic exercise will be performed in a semi-recumbent position, 3 times per week during the first two hours of haemodialysis. The initial prescription will be set in the moderate intensity range of 40-60% of peak aerobic capacity, progressing to 75% level by the end of the intervention. This exercise adoption phase aims to support patients in achieving the "average" target daily PA level within each intra-dialytic exercise session (21 minutes, continuous cycling, moderate intensity range or ~140 kcal/cycling session) and approximating 42% of the minimum weekly PA target. The exercise prescription will be individually increased through three additional phases of progression (months 2-4), behaviour development (months 5-6); and maintenance (months 7-9). The aim is for patients to increase exercise duration and intensity to expend around 185, 230, and 250 kcal per intra-dialytic exercise session respectively in each phase. Exercise duration and intensity will be regularly adjusted via ratings of perceived exertion, to ensure that the planned initial target volume of exercise (kcal per week) is "achieved" by all patients. These energy expenditure goals are deliverable via an increase in intra-dialytic cycling from 21 to 40 minutes, at moderate/vigorous exercise intensity, and will result in 55%, 69% and 75% respectively, of target weekly minimum PA volume being achieved. Twice per week, patients will also complete lower extremity muscular conditioning exercise, using ankle weights, after the aerobic cycling exercise. Drop-out rates for similar exercise training studies ranges from 17% to 25% (23) however all patients enrolled in the trial will be followed up to allow an intention to treat analysis.

We propose to employ physiotherapy assistants (PA, band 4 technical Instructors) in each region to deliver the intra-dialytic intervention. All PAs will be trained by the joint PI and regional coordinators, on how to standardise the delivery of the exercise prescription as well as how to record exercise prescription milestones, compliance behaviours, and any adverse outcomes. The proposed exercise intervention delivered this way would ensure appropriate and consistently applied progression of both the duration and intensity of the exercise training. Recent evidence from the British Renal Society Symposium revealed that successful patient compliance with and the effectiveness of intra-dialytic exercise training was enhanced by the involvement of a physiotherapy assistant in programme delivery (34). This role, supervised and quality assured by the regional coordinator, involves the technical implementation of the exercise prescription and associated protocols produced by the regional Research Assistant who will be blinded to treatment allocation.

4.6 Schedule of Assessment for each visit

Table 2. The range and phasing of PEDAL study assessment procedures

ASSESSMENT PROCEDURES					
	Timeline ± 1 week				
	Screening	Baseline	6 months	9 months	15 months
Informed Consent	X				
Inclusion/Exclusion Criteria	Х				
Medical History/Demographics	Х				
Adverse Events Recorded		Х	Х	Х	Х
Review/Record Medication		Х			
Anthropometric Measurements					
Height		Х	Х	Х	Х
Weight		Х	Х	Х	Х
Body Mass Index		Х	Х	Х	Х
Waist-to-Hip ratio		Х	Х	Х	Х
Quality of Life (and symptom					
burden) Assessments)					
* KDQOL		Х	Х	Х	Х
* EQ5D		Х	Х	Х	Х
Cardiovascular Assessments					
Resting Heart Rate		Х	Х	Х	Х
Resting Blood Pressure		Х	Х	Х	Х
Pulse Wave Velocity		Х	Х	Х	Х
Augmentation Index		Х	Х	Х	Х
Functional Capacity					
Measurements					
Peak Aerobic Capacity		Х	Х	Х	Х
(VO ₂ peak and/or Peak power output)					
Sit-to-Stand 60		Х	X	Х	Х
Functional Mobility (10mTUG)		Х	Х	Х	Х
* DASI questionnaire		Х	Х	Х	Х
* Tenetti Falls Efficacy Scale		Х	Х	Х	Х
Habitual Physical Activity					
GT3X Accelerometer		Х	Х	Х	Х
International Physical Activity		Х	Х	Х	Х
Questionnaire					
Routine Clinical Chemistry					
URR(5)		Х			
Blood lipid levels		X			
(LDL, HDL, triglyceride levels)					
Hb (and ESAs)		Х	Х	Х	X
HBA1c		X			,,
CRP		X			
Bicarbonate		X			
Phosphate		X	Х	Х	Х
Parathyroid hormone		X	X	X	X
		l			
Note: * o	denotes patient	t-reported out	come.		

4.7 End of Study Definition

The end of study is defined as the last participant's last visit (LPLV). The Sponsor, CI and/or the trial steering committee have the right at any time to terminate the study for clinical or administrative reasons. The end of the study will be reported to the Sponsor and REC within 90 days, or 15 days if the study is terminated prematurely. The Investigators will inform participants and ensure that the appropriate follow up is arranged for all involved. A summary report of the study will be provided to the Sponsor and the REC within 1 year of the end of the study.

4.7.1 Continuation of Intervention following the end of study

The study intervention will not be provided to participants routinely at the end of the study. Physicians caring for the study participant will make the decision whether or not to prescribe intra-dialytic exercise therapy to participants after their trial participation ends.

4.8 Subject Withdrawal

Any physician involved in the usual care of patients may withdraw patients from randomised treatment using their clinical judgment. This might occur due to the occurrence of an AE and the onset of symptoms that limit exercise tolerance. Patients withdrawn from randomised treatment will remain in the study for safety follow-up and subsequent events will be included in the ITT analysis but will be censored in the per-protocol analyses. If withdrawal is due to an AE it will be logged as such on the eCRF. All reasons for withdrawal will be noted in the participant's CRF and medical case notes.

4.8.1 Withdrawal of Consent to Follow-up

If at any time the patient formally withdraws his/her consent for future participation and disclosure of future information, no further evaluations will be performed and no additional data should be collected. Data collected before such withdrawal will be retained and used in the study analysis (with consent.)

4.8.2 Patient Retention

We will attempt to minimise the loss to follow-up in this study by (i) emphasising to participants the importance of their attendance at follow-up assessments even if they are no longer compliant with the intervention, (ii) reducing outcome assessment appointments to a maximum of four non-dialysis day visits, (iii) using a reminder protocol for non-dialysis day assessment appointments that utilises prompts via the dialysis unit staff, letters and telephone contact, (iii) providing travel remuneration (including, where necessary, taxi costs); (v) provision of training in issues related to compliance for all study staff who come in contact with the participants.

5.0 Safety

5.1 Definitions

Unexpected events that have not been defined as endpoints should be classified as either an SAE or AE depending on their severity. There is no requirement to report AE's. All SAEs must be recorded from the time at which the randomisation of the participant has occurred until the last study visit. The member of the research team should ask about the occurrence of SAEs at every visit during the study. Open-ended and non-leading verbal questioning of the participant should be used to enquire about AE/SAE occurrence. Participants should also be asked if they have been admitted to hospital, had any accidents, used any new medicines or changed concomitant medication regimens. If there is any doubt as to whether a clinical observation is an SAE, the event should be recorded. However, common symptoms in dialysis patients such as headache, nausea, itching etc., as well as infections not requiring hospitalisation, will not be recorded. Each initial SAE will be considered for severity, causality or expectedness and may be reclassified as a serious event or reaction based on prevailing circumstances.

A serious adverse event (SAE) is any AE that:

- results in death;
- is life threatening (i.e. the subject was at risk of death at the time of the event; it does not refer to an event which hypothetically might have caused death if it were more severe):
- requires hospitalisation or prolongation of existing hospitalisation;
- results in persistent or significant disability or incapacity;
- is a congenital anomaly or birth defect.

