5.3.1 Assessment of intensity

Mild: The subject is aware of the event or symptom, but the event or symptom is easily tolerated.

Moderate: The subject experiences sufficient discomfort to interfere with or reduce his or her usual level of activity.

Severe: Significant impairment of functioning; the subject is unable to carry out usual activities and/or the subject's life is at risk from the event

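### Section 5.1 separates SAE from AE by severity, while its own SAE definition rests on seriousness criteria, so the same event can be classed differently depending on which rule a site follows

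*Protocol*

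**What the plan says.** Protocol section 5.1 begins: "Unexpected events that have not been defined as endpoints should be classified as either an SAE or AE depending on their severity". The next sentence adds: "There is no requirement to report AE's". Every SAE, by contrast, must be recorded from randomisation to the last study visit.

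The same section then gives a formal definition, introduced by "A serious adverse event (SAE) is any AE that" and followed by five criteria: death, threat to life, hospitalisation, disability or incapacity, and congenital anomaly. The third reads "requires hospitalisation or prolongation of existing hospitalisation". None of the five sets a level of intensity.

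Severity also appears in 5.1 as an attribute judged after an event has entered the SAE process: "Each initial SAE will be considered for severity, causality or expectedness and may be reclassified as a serious event or reaction". Section 5.3.1, headed as an assessment of intensity, provides a scale of mild, moderate and severe. Its top grade is "Severe: Significant impairment of functioning; the subject is unable to carry out usual activities and/or the subject's life is at risk from the event".

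Section 5.2 requires SAEs to reach the Clinical Trials Unit within 7 days with a causality assessment. Section 5.3 asks investigators to report every unexpected adverse event, serious or otherwise. Section 6.4 tabulates SAEs by system organ class and body system.

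**The concern.** Seriousness and severity are different properties. Seriousness concerns what an event led to. Severity concerns how intense it was. Section 5.1 uses the second as its sorting rule and the first as its definition, so it gives a site two criteria for one decision.

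The decision matters because it determines which events enter the 7-day reporting route in 5.2 and the table in 6.4. That table is the main planned display for secondary objective iii, which asks whether exercise brings an excess of adverse events. If one site sorts by intensity and another by the list, the tabulated SAEs are not the same kind of event across sites.

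**Working it through.** No arithmetic applies. The protocol gives no SAE rate and no split by intensity, so the check sets the texts side by side.

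**Step 1: what the opening sentence covers.** It is limited to unexpected events that are not endpoints. Section 2.1.4 lists all hospitalisations, all-cause mortality and cardiovascular mortality as secondary endpoints. Admissions and deaths therefore fall outside the opening sentence on its own terms. Prolongation of an existing stay is not clearly covered by that endpoint.

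**Step 2: what severity can mean.** Section 5.1 does not define it. Section 5.3.1 is the only graded scale of this kind in the protocol, and 5.1 names severity beside causality, for which 5.3.2 supplies a scale. A site could reasonably turn to 5.3.1, although no sentence links the two.

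**Step 3: compare each SAE criterion with the 5.3.1 grades.**

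| SAE criterion in 5.1 | Can it be met at mild or moderate intensity? | Do the two rules diverge? |
|---|---|---|
| Death | No in practice; life at risk is graded severe | No; also an endpoint |
| Life-threatening | No; life at risk is graded severe | No |
| Hospitalisation | Yes; the scale does not mention admission | Admissions are endpoints, so outside the opening sentence |
| Prolongation of existing stay | Yes | Yes: SAE by the list, AE by the opening sentence |
| Disability or incapacity | Largely overlaps the severe grade | Little |
| Congenital anomaly | Yes; the grade is not tied to it | Yes in principle |

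**Step 4: the opposite direction.** Take a short-lived symptom that stops usual activities but needs no admission, threatens no life and leaves no lasting disability. Under 5.3.1 it is severe: "Severe: Significant impairment of functioning; the subject is unable to carry out usual activities". By the opening sentence it is an SAE. By the list it is not, since it meets none of the five criteria.

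**Step 5: what happens to an event sorted as an AE.** Section 5.1 says it need not be reported. Section 5.3 says every unexpected event is reported whatever its seriousness. These two statements also conflict. The heading of 5.3 refers to serious events only, which leaves its intended reach unclear.

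The two rules in 5.1 therefore disagree in both directions, for a limited set of events.

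**The case against.** The strongest reply is that severity in the opening sentence is a loose word for the list below it. Section 5.3.1 is headed intensity, 5.1 does not refer to it, and the explicit definition in the same section would normally govern. That reading is plausible, and a careful site would probably adopt it. It does not remove the defect, because 5.1 also uses severity as a separate attribute of an event already called an SAE. The section never says which sense applies in its first sentence.

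A reader might go further and infer that serious events of low intensity would vanish from the trial's data. The documents do not support that:

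- Section 5.3 asks for all unexpected events.
- Section 5.1 tells sites to record an event when in doubt, and to ask participants about admissions.
- Table 2 schedules adverse event recording at baseline, 6, 9 and 15 months.
- Hospitalisations and deaths are collected as endpoints.

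These provisions make total loss unlikely. They do not settle whether an event takes the SAE route. The instruction on doubtful events helps only a site that has a doubt, and collecting admissions as an endpoint does not by itself attach the 5.2 causality assessment or the 6.4 coding.

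A reader might also infer from the sentence on reclassification that intensity can downgrade an SAE. It cannot be read that way: the stated destination is a serious event or reaction, and no downgrade is described.

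**Conclusion.** The contradiction in 5.1 is real and concerns the rule that defines the trial's tabulated safety outcome. Its consequence is possible inconsistency between sites in SAE reporting and in the SAE table. This rests on one assumption: that some sites would apply the opening sentence literally, using the 5.3.1 scale or something like it.

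The size cannot be stated. Any count of affected events would need an SAE rate and an intensity split, neither of which the protocol gives. It would also have to leave out the admissions and deaths that the opening sentence does not cover. A reader might suspect that the ambiguity inflates SAEs in the exercise arm in particular. Participants and physiotherapy assistants are unblinded, so differential use is conceivable, but nothing in the protocol shows its direction or that it would occur.

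The primary endpoint, its analysis, the significance level and the sample size are unaffected. The point deserves correction because the wording is plainly inconsistent and cheap to mend.

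**What to change.** Make three changes in one edit of section 5:

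1. In the first sentence of 5.1, make the sorting rule the seriousness criteria listed below it, irrespective of intensity, in place of severity.
2. State that the 5.3.1 rating only describes an event and does not decide whether it is serious.
3. Reconcile the statement in 5.1 that AEs need not be reported with the requirement in 5.3 to report all unexpected adverse events, so that sites have one reporting rule.

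The first two changes cost a few sentences in the protocol and a note to sites, with no new data items or staff. The third also needs only wording, but the trial team must first decide which reporting scope was intended.

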2.1.2 Secondary Objectives

- To determine, in comparison to usual care, whether usual care augmented by intra-dialytic exercise training improves the physical function of stage 5 CKD patients receiving maintenance haemodialysis renal replacement therapy
- ii. To compare the effect of usual care augmented intra-dialytic exercise training versus usual care on systemic and biochemical markers of vascular and cardio-metabolic health of stage 5 CKD patients receiving maintenance haemodialysis renal replacement therapy
- To assess, in comparison to usual care, whether usual care augmented by intra-dialytic exercise training is associated with an excess of adverse events in stage 5 CKD patients receiving maintenance haemodialysis renal replacement therapy

- iv. To explore and document the views of participants and members of the renal care teams in relation to their experiences of usual care and intra-dialytic exercise-augmented usual care
- v. To estimate the cost-effectiveness of augmenting, with intra-dialytic exercise training, the usual care stage of 5 CKD patients receiving maintenance haemodialysis renal replacement therapy

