2.1.4 Secondary Endpoint

Assessed at 6, 9 and 15 months. Change between baseline and follow-up for:

- KDQOL-PCS
- KDQOL-MCS
- KDQOL-Vitality subscale
- KDQOL- symptom burden subscale
- IPAQ
- Height (at screening visit only), Weight and anthropometric (BMI, waist to hip ratio)
- Peak aerobic capacity
- Duke Activity Status Index (self-report 12-item activity of daily living questionnaire)
- 10m Timed-up-and-go (composite test of leg strength, balance, coordination and gait speed)
- Sit-to-stand 60 (proxy measure of lower extremity muscular endurance)
- Tinetti Falls Efficacy Scale
- Habitual physical activity (a self-report assessment via International Physical Activity Questionnaire)
- Habitual physical activity (GT3X tri-axial accelerometer)
- Arterial stiffness (via pulse wave velocity and augmentation index)
- Blood pressure
- Hb
- ESAs
- Phosphate
- Parathyroid hormone (PTH)
- EQ-5D, a generic multi-attribute health related QOL questionnaire for use in cost utility analysis.
- Health Economic questionnaire regarding resource use
- All hospitalisations
- All-cause mortality
- Cardiovascular mortality
- Safety / Harms (SAE)

Qualitative Study and analysis

A constructivist phenomenological approach will be used to learn about views and perceptions of participants and build greater understanding of varied perspectives of both service users and providers (Crotty 1998; Grbich 1999). Focus groups and individual interviews will be used as most appropriate to the stage of the study and location of data collection. All participants in the pilot study and RCT will be eligible for inclusion in the qualitative sub-study. Purposive sampling will be used to ensure varied experiences and viewpoints are represented, for example, including service users and providers from different study regions, including people in both study arms, and aiming to include people with different participation rates and response to the intervention. Appropriate topic guides will be developed for pilot study and RCT, and for service users and providers; questions will be discussed within the project team and steering group.

Health Economic analysis

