5.3 Reporting Unexpected Serious Adverse Events

Investigators will make their reports of all unexpected adverse events, whether serious or not, to the Glasgow Clinical Trials Unit.

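### Protocol section 5 contradicts itself on reporting non-serious AEs and on whether endpoint deaths and hospitalisations are SAEs, and objective iii is wider than the SAE-only endpoint and analysis

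*Protocol*

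**What the plan says.** **Reporting of AEs.** Section 5.1 says "There is no requirement to report AE's". Section 5.3, although headed as concerning serious events, says "Investigators will make their reports of all unexpected adverse events, whether serious or not, to the Glasgow Clinical Trials Unit". Table 2 in section 4.6 has a row "Adverse Events Recorded", marked at baseline, 6, 9 and 15 months. Section 4.8 logs on the eCRF any AE that causes withdrawal from randomised treatment.

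**What counts as an SAE.** Section 5.1 opens with "Unexpected events that have not been defined as endpoints should be classified as either an SAE or AE depending on their severity". It goes on to require that every SAE be recorded from randomisation to the last visit, and it lists five SAE criteria, among them death and new or prolonged hospitalisation. Section 2.1.4 lists "All hospitalisations", all-cause mortality, cardiovascular mortality and SAEs as secondary endpoints.

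**What follows from SAE status.** Section 5.2 requires a report to the trials unit within 7 days with a site causality assessment. Confirmed unexpected SAEs are notified to the sponsor, the ethics committee and the DSMC. Section 6.4 tabulates SAEs by system.

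**The objective.** Secondary objective iii in section 2.1.2 asks whether exercise added to usual care "is associated with an excess of adverse events in stage 5 CKD patients".

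**Exercise staff.** Section 4.5.2 says the physiotherapy assistants who deliver the exercise are trained to record exercise milestones, "compliance behaviours, and any adverse outcomes".

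**The concern.** A site cannot follow both 5.1 and 5.3 for an unexpected, non-serious event. If sites resolve the conflict differently, the non-serious AE data will not be comparable across sites. A statistical analysis plan cannot repair this, because it governs analysis and not what sites collect.

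The endpoint exclusion matters for oversight. Section 6.5 plans no formal interim analysis and relies on committee review of unblinded safety data. Whether a death or an admission is processed as an SAE, with prompt reporting and a causality judgement, should not depend on how a site reads one clause.

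Objective iii is a between-arm harms question. Its wording covers all adverse events, but the protocol secures data only for serious ones.

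**Working it through.** The protocol states no figure on this point that could be reproduced. The check is a comparison of texts, with one side calculation.

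**Step 1: non-serious, unexpected event.**
- Section 5.1: no report required.
- Section 5.3: report to the trials unit, serious or not.
- Result: direct contradiction.
- Table 2 and section 4.8 speak of recording or logging. That can be squared with a waiver of reporting, so they add uncertainty but are not clearly a second contradiction.

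**Step 2: death or hospitalisation.**
- Section 2.1.4: both are endpoints.
- Section 5.1, opening sentence: endpoint events are outside SAE/AE classification.
- Section 5.1, SAE list: both are SAE criteria (two of five), and all SAEs must be recorded.
- Result: the section both excludes and includes them. On the literal exclusion, the SAE table would hold only events that meet one of the other three criteria (life-threatening, disabling, congenital) without death or admission. Because SAEs are themselves listed as an endpoint, the literal rule is also circular and would exclude even those.

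**Step 3: objective against endpoint and analysis.**
- Section 2.1.2: adverse events.
- Section 2.1.4: SAEs.
- Section 6.4: SAEs tabulated, no AE comparison stated.
- Section 5.1: AE reporting waived, and common dialysis symptoms and infections without admission not recorded.
- Result: the objective is wider than the data and analysis that support it.

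**Step 4: contact by arm.**
- Inputs: three exercise sessions a week (section 4.5.2) for 9 months.
- 9 × 365.25 / 12 / 7 = 39.1 weeks, and 39.1 × 3 = about 117 scheduled exercise sessions per EXHD participant. This is an upper figure, since section 6.6 expects 17-25% to discontinue. UCHD has no exercise-session counterpart.
- Sources not limited to one arm: assessment visits at 6, 9 and 15 months with SAE enquiry (section 5.1), a monthly patient questionnaire during dialysis on health care use, and hospital admissions from clinical records (both in the health economic text of section 2.1).
- Illustration, with detection rates that are assumptions and not in the protocol. With equal true risk, the apparent risk ratio is detection in EXHD divided by detection in UCHD. At 0.90 in EXHD:
  - UCHD 0.90: 0.90/0.90 = 1.00
  - UCHD 0.80: 0.90/0.80 = 1.125
  - UCHD 0.70: 0.90/0.70 = 1.29
  - UCHD 0.60: 0.90/0.60 = 1.50
  - UCHD 0.50: 0.90/0.50 = 1.80
- This concerns non-serious events only. It does not apply to deaths, or to admissions found from records in both arms.

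**The case against.** The strongest reply is that this is loose drafting with an obvious intended meaning. Section 5.1 says all SAEs are recorded, names death and hospitalisation as criteria, tells staff to ask about admissions, and says doubtful events should be recorded. A literal exclusion would empty section 5, so it cannot be intended. Deaths and admissions are endpoints in any case, and the independent committee sees unblinded safety data (sections 6.5 and 9.5). The planned harms endpoint and tabulation are already SAE-only, and the primary endpoint, its analysis and the sample size are untouched.

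Most of this stands, and it limits the severity. It does not remove the conflict between 5.1 and 5.3, nor tell a site whether an endpoint admission needs a seven-day report.

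A reader might go further in three ways that the protocol does not support.

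- **That deaths and admissions are lost.** They are not: they remain secondary endpoints, and admissions also come from clinical records. Only the reporting route and the SAE table are in doubt.
- **That exercise staff log events in one arm only.** No section says so. The assistants' recording duty is attached to delivering the exercise, so fuller ascertainment in EXHD is a plausible inference, but SAE enquiry is set for all participants.
- **That the harms objective cannot be answered without bias.** Deaths, admissions from records, and SAEs asked about at common visits can be compared between arms. The protocol plans no between-arm test of events noted at exercise sessions, and any particular rate ratio from unequal detection would rest on assumed inputs.

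**Conclusion.** The point holds as a contradiction within section 5 and a mismatch between objective iii and its endpoint and analysis. It should be fixed, but it does not threaten the trial's primary result. Its reach is two of the five SAE criteria, whose reporting route and place in the SAE table are ambiguous, and all non-serious AEs, whose collection is unsettled. The contradictions rest on the text alone.

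Unequal ascertainment is a secondary caution for non-serious events. It depends on the inference that assistants' session contact raises detection in EXHD. The apparent risk ratios of 1.00 to 1.80 show what the assumed detection rates would do; they are not estimates for this trial.

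**What to change.** 1. Remove or reword the endpoint exclusion in section 5.1, so that deaths and hospitalisations meeting that section's SAE definition are also recorded and reported as SAEs, as well as being counted as endpoints.
2. Reconcile sections 5.1 and 5.3, and Table 2, on whether non-serious AEs are recorded, reported, both or neither.
3. Align objective iii with the SAE endpoint and analysis. If non-serious AEs are to be kept in the objective, collect them by the same method and at the same times in both arms.
4. Base the between-arm harms comparison on sources common to both arms: study-visit enquiry, clinical records and the monthly questionnaire. Report events noted by physiotherapy assistants during exercise sessions separately, as a description of EXHD.

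The cost is a short amendment and slightly more SAE paperwork. Choosing the second option in item 3 would add some data collection, for which the monthly questionnaire is a ready vehicle.
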